		Study	Stroma (%)	Epithelium (%)	Lumen (%)
Normal Peripheral Zone Tissue	Langer et al 2010	38.2	31.2	29.6	
	Chatterjee et al 2016	38.3±1.4	32.0±1.5	30.1±1.2	
	HM-MRI	39.0±13.6	21.5±4.6	39.4±14.1	
Prostate Cancer	Langer et al 2010	38.6	46.2	13.5	
	Chatterjee et al 2016	27.9±1.0	60.9±1.9	11.2±1.1	
	HM-MRI	37.2±9.1	48.8±9.2	14.0±5.2	

PCa from normal tissue was 0.99 for epithelium, 0.80 for lumen, 0.79 for stroma, and 0.71 for T_2 (AUC for ADC was not evaluated because cancer ROIs were outlined in ADC maps). These results suggest that HM-MRI non-invasively provides 3-dimensional information that is similar to the information obtained from 2D *ex vivo* histology slices, and that prostate tissue composition measured non-invasively by using HM-MRI have potential to improve PCa diagnosis and assessment of PCa aggressiveness. The study also resulted in a filed patent application (30).

A.3.2. PCa risk maps derived from quantitative MRI data

We have developed a preliminary risk map based on mpMRI: ADC, T_2 , and DCE signal enhancement rate (α). These parameters were calculated on a voxel-by-voxel basis for the entire, co-registered prostate. Each parameter was normalized (to 0-100) with low T_2 , low ADC, and high α signify high risk. The final risk score is a weighted sum of the parameters (ADC 40%, T_2 40%, DCE 20%) with higher risk for low T_2 , low ADC, and high α values. We analyzed preoperative 3T mpMRI of 22 PCa patients, and used five patients as the training set to find the optimal threshold for predicting PCa and 17 patients as the test set. A sector-based analysis (18 sectors per prostate) on the 17 test patients showed the following PCa detection performance: sensitivity 75% (105/140), specificity 89% (147/166), positive predictive value 85% (105/124), negative predictive value 81% (147/182), and AUC 0.82 (95% CI [0.77, 0.87]). Importantly, the risk map correctly identified all index lesions. This study suggests that the risk map can detect PCa and guide targeted biopsies for improved PCa diagnosis.

A.3.3. Pilot DSS study:

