The major goal of this study is to compare the accuracy of the Risk Map DSS tool against the clinical accuracy of experienced radiologists in the context of the reference standard of biopsy histology. The primary endpoints will be ROC curve, AUC value, the secondary endpoint will be sensitivity, specificity, PPV, and NPV, and the tertiary endpoint will be correlation strength between the DSS tool output and tumor-specific Gleason scores. Both per-patient and per-tumor analyses will be conducted. For the per-patient analysis, patients who are diagnosed with PCa from the biopsy procedure will be considered as positive for PCa, and patients who are not diagnosed with PCa from the biopsy procedure will be considered as negative for PCa. For the per-tumor analysis, each individual PCa tumor diagnosed from the biopsy procedure will be analyzed separately, and biopsy sites that do not yield PCa diagnosis will be considered as negative for PCa. To ascertain a true positive biopsy, the finding and the biopsy must match in sextant and zone. If ambiguity in biopsy site arises with regard to indications from the DSS tool, or the radiologist's opinion, and the biopsy, expert radiologist ([name]) and pathologist ([name]) will review each case to make the determination. This will allow us to calculate the performance of: (1) the Risk Map DSS tool, (2) the radiologist, and (2) the standard sextant biopsy. We will evaluate these performance endpoints on clinically significant PCa (but we will have data for all tumors). Spearman correlation coefficient will be estimated in the usual manner.

C.4. Statistical power consideration

We expect the following level of performance: AUC 0.90±0.03, sensitivity 90±5%, specificity 90±4%, and statistically significant (Spearman's) correlation strength of 0.8 with tumor-specific Gleason scores. Variances are estimated based on the expectation of PCa diagnosis in 35% of 125 patients, and based on an empirical rule-of-thumb formula

for AUC and binomial probability for sensitivity and specificity. The estimated 95% confidence intervals (CIs) are: for AUC [0.87, 0.93], for sensitivity [0.85, 0.95], and for specificity [0.86, 0.94]. These uncertainty estimates do not include analysis of biopsy by sextant and zone of the 12-20 cores per patient; estimates of 12 by-location-analyses per patient reduce all uncertainties to about 1%. These estimates suggest that this protocol will produce meaningful performance estimates.

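### C.4 labels roughly one standard error as a 95% confidence interval, so the stated precision for AUC, sensitivity and specificity is far too favourable

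*Combined protocol and SAP*

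**What the plan says.** C.4 (Statistical power consideration) gives three expected values with margins: "AUC 0.90±0.03, sensitivity 90±5%, specificity 90±4" per cent. On the method it says: "Variances are estimated based on the expectation of PCa diagnosis in 35% of 125 patients". An unnamed rule of thumb is used "for AUC and binomial probability for sensitivity and specificity". The same margins then return under another label: "The estimated 95% confidence intervals (CIs) are: for AUC [0.87, 0.93], for sensitivity [0.85, 0.95], and for specificity [0.86, 0.94"]. For the analysis by location it adds that "estimates of 12 by-location-analyses per patient reduce all uncertainties to about 1" per cent. From these figures C.4 concludes that the performance estimates will be meaningful.

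C.3 makes the ROC curve and AUC primary and sensitivity and specificity secondary. It also says: "We will evaluate these performance endpoints on clinically significant PCa (but we will have data for all tumors").

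The one operating point reported for a risk map is in A.3.2: "sensitivity 75% (105/140), specificity 89% (147/166"), with "AUC 0.82 (95% CI [0.77, 0.87"]). It was analysed by sector in 17 test patients.

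**The concern.** C.4 uses identical ranges first as ± margins and then as 95% limits. If the margins are standard errors, the limits should be about twice as wide. These are the only precision figures the protocol gives for 125 patients, and its conclusion about useful precision rests on them. A reader would take it that sensitivity will be known to within 5 points and AUC to within 0.03.

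There is also a question of how the three expected values relate. C.4 does not say how they were chosen, and names neither a threshold nor an ROC model. If the true sensitivity at the working threshold is below 90%, its interval widens further.

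**Working it through.** **Inputs (C.4).** Positives: 0.35 × 125 = 43.75. Negatives: 0.65 × 125 = 81.25. Expected AUC, sensitivity and specificity are each 0.90, with binomial variance for the last two.

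**Step 1: reproduce the ± values.**
- Sensitivity: SE = √(0.9 × 0.1 / 43.75) = 0.0454, which rounds to the stated 5 points.
- Specificity: SE = √(0.9 × 0.1 / 81.25) = 0.0333; C.4 states 4 points.
- AUC: the rule of thumb is not named, so Hanley–McNeil is assumed. With a = 0.9/1.1 = 0.8182 and b = 2 × 0.81/1.9 = 0.8526, SE = √{[0.09 + 42.75(a − 0.81) + 80.25(b − 0.81)] / (43.75 × 81.25)} = 0.0330, which rounds to the stated 0.03.

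The margins therefore come back as about one SE. The by-location claim shows the same pattern: 4.54/√12 = 1.3 points and 3.33/√12 = 1.0 point, again one SE, and only if the 12 locations in a patient are independent.

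**Step 2: 95% limits from the same inputs (1.96 × SE).**

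| Measure | Stated 95% CI | 95% half-width | Recomputed 95% CI | Nominal coverage of stated interval |
|---|---|---|---|---|
| Sensitivity | [0.85, 0.95] | 0.089 | about [0.81, 0.99] | 0.05/0.0454 = 1.10 SE, 73% |
| Specificity | [0.86, 0.94] | 0.065 | about [0.83, 0.97] | 0.04/0.0333 = 1.20 SE, 77% |
| AUC | [0.87, 0.93] | 0.065 | about [0.84, 0.96] | 0.03/0.0330 = 0.91 SE, 64% |

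The exact (Clopper–Pearson) interval for 40/44 is [0.78, 0.97]. A binormal variance formula for AUC gives SE 0.037 and half-width 0.072. The crude √(0.9 × 0.1/125) gives SE 0.027 and half-width 0.053. Under each of the three AUC formulas the half-width is well above 0.03.

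For scale, a true ±5 points at 90% sensitivity needs 1.96² × 0.09/0.05² = 138.3 positives, or 138.3/0.35 = about 395 patients.

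**Step 3: do the three expected values fit together?**
- Single cut: AUC = (0.90 + 0.90)/2 = 0.90, an exact fit.
- Equal-variance binormal curve with AUC 0.90: separation √2 × 1.2816 = 1.812, so sensitivity at 90% specificity is Φ(1.812 − 1.282) = 0.70.
- Equal-variance binormal curve through 90%/90%: separation 2 × 1.2816 = 2.563, so AUC = Φ(2.563/√2) = 0.965.
- Varying the ratio of the two standard deviations from 0.3 to 3 moves the 0.70 to between 0.57 and 0.82, and the 0.965 to between 0.945 and 0.965.

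**Step 4: sensitivity precision if 90% is optimistic.** Half-width = 1.96 × √(p(1 − p)/43.75).

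| Sensitivity p | SE (points) | 95% half-width (points) |
|---|---|---|
| 0.70 | 6.9 | 13.6 |
| 0.75 | 6.5 | 12.8 |
| 0.85 | 5.4 | 10.6 |
| 0.90 | 4.5 | 8.9 |

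**The case against.** The ± notation is a fair way to show standard errors, and as standard errors the figures are roughly right. C.4 specifies no hypothesis test, so no power calculation fails. That limits the consequence, but it does not rescue the sentence that calls these ranges 95% confidence intervals.

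Two stronger readings are tempting, and the documents support neither.

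*That 90% sensitivity, 90% specificity and AUC 0.90 cannot occur together.* They can. A yes/no reading gives exactly these values, and a non-concave curve also allows them. C.4 states no ROC model, and the 70% figure depends on the model assumed. What stands is that a usual smooth concave curve for a graded score does not produce this combination.

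*That the pilot refutes 90% sensitivity, or that 70–75% should replace it.* The pilot's 75% counts sectors in 17 patients and comes from a score that included DCE. C.4's variances are per patient, and the tool under test is described in section B as expanded and built on ADC, T2 and tissue composition maps. A.3.2 also reports that no index lesion was missed. The pilot's own AUC fits a single cut, (0.750 + 0.886)/2 = 0.818. An equal-variance binormal curve with AUC 0.82 would predict only about 54% sensitivity at that specificity, against the 75% observed. The ROI-level AUCs in A.3.4 (0.88 to 0.96) do not settle the matter either: under the same binormal model, AUC 0.95–0.96 puts the equal sensitivity/specificity point at about 0.88–0.89. The pilot thus gives no support for 90% per-patient sensitivity, but it does not contradict it.

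Nor does doubt about 90% explain the narrow interval. The interval is too narrow even when 90% is accepted in full.

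**Conclusion.** The concern holds as a labelling error with a clear size. On C.4's own inputs the 95% half-widths are about 1.8 times the stated margin for sensitivity (8.9 against 5 points), 1.6 times for specificity (6.5 against 4 points) and 2.2 times for AUC (0.065 against 0.03). The binomial results need no assumption beyond C.4's prevalence and expected values. The AUC result assumes Hanley–McNeil, with 0.053 to 0.072 under the alternatives tried.

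The mismatch between AUC and operating point is secondary and depends on the model. It justifies showing a range for sensitivity, not a new expected value.

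One further uncertainty cannot be sized from the documents. The 35% refers to any PCa diagnosis, while C.3 evaluates the endpoints on clinically significant PCa. At 90% sensitivity the half-width is 1.96 × 0.3/√n = 0.588/√n, so fewer positives would widen it beyond ±9 points.

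**What to change.** In C.4:

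1. Replace the three intervals with correct 95% intervals: sensitivity about [0.81, 0.99] (or exact, [0.78, 0.97] for 40/44), specificity about [0.83, 0.97], AUC about [0.84, 0.96]. Alternatively, keep the ± values and call them standard errors. Treat the by-location figure the same way and state its independence assumption.
2. Name the AUC variance formula.
3. Say how the three expected values were derived and at what threshold, and add sensitivity precision over a range such as 70–90% (95% half-width about ±13.6 to ±9 points).
4. Rest the conclusion that the estimates will be meaningful on the corrected widths.

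This costs a few lines of text and no extra patients. The only downside is that the stated precision becomes less favourable.

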We will test an artificial intelligence-based Risk Map DSS tool we have developed, which is based on and expanded from previously identified key MR image features that are effective for identifying PCa from normal prostate tissue, and which also correlates moderately with Gleason scores (ADC, T2, and tissue composition maps). The DSS tool will assist radiologists interrogate suspicious areas in the prostate that are potentially clinically significant PCa foci, and will identify up to two potential clinically significant tumor sites. In addition to systematic biopsies and the targets identified by the radiologist, up to two targets determined by the DSS tool will be biopsied. Biopsy histology results of all cores will be used as the reference standard to evaluate the performance of the Risk Map DSS tool.

C. METHODOLOGY

C.1. Study Design:

This is a prospective, single-arm, unblinded study of patients with known or suspected prostate cancer. A total of 125 patients will be enrolled.

Recruitment: We will recruit patients with known or suspected prostate cancer who have been referred to the Department of Radiology at the University of Chicago Medical Center for a diagnostic MRI exam of the prostate, to be followed by an MRI-guided fusion biopsy of the prostate, per standard clinical protocol.

All patients will be scanned using a standard clinical prostate MRI protocol. Research sequences will be added to the routine clinical exam. The research sequences will not exceed 15 minutes. The patients will not receive intravenous contrast agent as part of the research protocol.

All patients will then undergo a 12-core TRUS-guided or transperineal US-guided sextant random biopsy by their urologist at the Urology Clinic as their standard of care treatment. Additional biopsy targets may be selected based on an expert radiologist's interpretation of the patient's clinical MRI, as part of the clinical, standard of care MR targeted biopsy procedure. Up to two additional biopsy targets per patient will be selected by the Risk

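### C.4's 95% interval for patient-level specificity, [0.86, 0.94], is too narrow for about 81 men without a cancer diagnosis, and the 90% it is centred on has no patient-level support in the documents

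*Combined protocol and SAP*

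**What the plan says.** Section C.1 fixes the sample: "A total of 125 patients will be enrolled". Section C.4 then describes the precision expected from that number: "We expect the following level of performance: AUC 0.90±0.03, sensitivity 90±5%, specificity 90±4" (the last three in per cent). The basis is "Variances are estimated based on the expectation of PCa diagnosis in 35% of 125 patients", with a binomial formula for sensitivity and specificity, and the 95% confidence interval given for specificity is [0.86, 0.94]. C.4 adds that these figures leave out the analysis by biopsy location, and that twelve location analyses per man would bring all uncertainties down to about 1%.

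Section C.3 defines the negatives for the per-patient analysis: "patients who are not diagnosed with PCa from the biopsy procedure will be considered as negative for PCa".

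The only specificity observed in the preliminary work is in A.3.2. The sample is described as "We analyzed preoperative 3T mpMRI of 22 PCa patients", of whom five served for training. The result is introduced with "A sector-based analysis (18 sectors per prostate) on the 17 test patients showed the following PCa detection performance", and the figure is "specificity 89% (147/166" sectors). C.4 does not cite this result, or any other, as the source of its 90%.

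**The concern.** Two things about the patient-level specificity in C.4 do not stand up.

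The first is the width. A 95% half-width of 4 points looks too small for a proportion near 90% estimated on about 81 men. C.4 concludes from its intervals that the protocol will give meaningful estimates, so a reader will take [0.86, 0.94] as the precision to expect.

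The second is the centre. The only figure in the documents that resembles 90% has a different unit (the sector) and a different control group (benign sectors in glands that contain cancer). The other preliminary studies (A.3.1, A.3.3, A.3.4) compare cancer with normal-tissue regions and report AUCs and correlations. No specificity in men without cancer is reported anywhere. A reader who assumes that the pilot 89% stands behind the 90% would be moving a sector rate to patients without a stated basis.

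A related problem affects the 1% quoted for the location-level analysis, if it treats several locations in one man as independent observations.

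**Working it through.** **Inputs.** Total 125 (C.1). Diagnosis expected in 35% (C.4). Expected specificity 0.90, binomial variance, 95% level (C.4; taken as two-sided, since sidedness is not stated). Twelve locations per man (C.4). Pilot counts 105/140 and 147/166, 18 sectors, 17 test patients (A.3.2).

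**1. Number of negatives.** 0.65 × 125 = 81.25, about 81 men.

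**2. Can the stated ±4 points be reproduced?**
- SE = √(0.90 × 0.10 / 81) = 0.033.
- 95% half-width = 1.96 × 0.033 = 0.065, giving about [0.83, 0.97].
- For 73/81, Wilson gives [0.817, 0.949] and Clopper-Pearson [0.815, 0.956].
- None of these gives a half-width of 0.04. The stated ±4 is 0.04/0.0333 = 1.2 standard errors, with nominal coverage of about 77%. It is closer to a standard error than to a 95% half-width. The same holds for sensitivity: √(0.09/44) = 0.045 against a stated ±5 points.

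**3. What would ±4 points require?**
- At 90%: 1.96² × 0.09 / 0.04² = 216 negatives, or 216/0.65 = about 332 patients.
- With 81 negatives, specificity would have to be about 96.5%: 1.96 × √(0.965 × 0.035 / 81.25) = 0.040.

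**4. Half-width at other values of specificity (n = 81, Wald).**

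| Specificity | 95% half-width | 95% interval |
|---|---|---|
| 0.90 | 6.5 points | [0.83, 0.97] |
| 0.80 | 8.7 points | [0.71, 0.89] |
| 0.70 | 10.0 points | [0.60, 0.80] |
| 0.60 | 10.7 points | [0.49, 0.71] |
| 0.50 | 10.9 points | [0.39, 0.61] |

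**5. Unit of the pilot specificity.** 17 × 18 = 306 = 140 + 166, so 147/166 = 0.886 counts sectors. All the men had cancer, so the 166 negatives are sectors without cancer inside affected glands.

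**6. Does 0.886 per sector fix a per-patient value?** This needs a rule for calling a man positive and a within-man correlation r. The documents give neither, so both are assumed here, with exchangeable normal sector scores and 18 sectors.
- Positive if any sector is flagged: per-patient specificity is 0.886^18 = 0.11 at r = 0, rising to 0.66 at r = 0.8.
- Positive if at least 4 of 18 sectors are flagged: 79% to 86% over the same range of r.

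The answer moves from 11% to 86% on inputs that the documents leave open.

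**7. The 1% at location level.** With 81 × 12 = 972 locations treated as independent, SE = √(0.09/972) = 0.0096, which matches C.4. With intraclass correlation ρ (not given; a range is assumed), the variance is multiplied by 1 + 11ρ:

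| ρ | Multiplier | SE | 95% half-width |
|---|---|---|---|
| 0 | 1.0 | 1.0 point | 1.9 points |
| 0.3 | 4.3 | 2.0 points | 3.9 points |
| 0.5 | 6.5 | 2.5 points | 4.8 points |
| 1 | 12.0 | 3.3 points | 6.5 points |

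The 1% is therefore a standard error, and it holds only if locations within a man are independent. This table counts only locations in men without a diagnosis; benign sites in the other men would add to the denominator.

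**The case against.** C.4 presents 90% as an expectation. It does not say that the value comes from A.3.2, so the documents do not contradict themselves. Nor does C.4 derive 125 from specificity; it describes precision at a number already fixed. The tool under test also differs from the pilot map, which was a fixed weighting of ADC, T2 and DCE with a threshold found in five patients. The trial tool is AI-based and adds tissue composition maps, so it may do better. Specificity is a secondary endpoint, and replacing 0.90 by 0.886 hardly changes the standard error (0.035 against 0.033). All of this stands. It limits the point about the centre to an unsupported assumption, but it does not rescue the width, which fails at C.4's own 90%.

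A reader might go further and infer that per-patient specificity must fall far below 90%, because a man has many sectors in which a false flag can occur. The documents do not support that: C.3 states no patient-level calling rule, and step 6 shows how strongly the result depends on one.

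A reader might also infer that holding specificity at 90% would push per-patient sensitivity down to 33–53%. That range assumes one or two positive sectors per man, whereas the pilot averaged 140/17 = 8.2. At eight sectors the same kind of model gives 72–91%, which includes the stated 90%.

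Finally, C.3 evaluates the endpoints on clinically significant cancer, while the 35% in C.4 refers to any cancer diagnosis. The number of negatives is therefore itself uncertain; 81 is the number that C.4's own basis implies.

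**Conclusion.** The point holds for the stated precision and for the missing basis of the 90%.

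- **Width.** With 81 negatives and specificity of 90%, the 95% half-width is 6.5 points against the 4 stated. It grows to about 11 points if specificity is 0.5 to 0.6. This rests only on C.4's own inputs and the binomial formula it names.
- **Centre.** The 90% is a patient-level assumption. The documents contain no per-patient specificity and no data on specificity in men without cancer. The pilot 89% neither confirms nor refutes it. The true patient-level value is unknown, which is weaker than saying that it will be low.
- **Location level.** The 1% is a standard error under independence within a man, an assumption that C.4 neither states nor supports.

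The consequence is overstated precision for a secondary endpoint. The sample size, the data collected and the primary ROC/AUC endpoint are not affected by this point.

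**What to change.** In C.4:

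1. Replace the specificity interval with about [0.83, 0.97] at the assumed 90% on about 81 negatives.
2. Add a range for lower values, as in step 4, with a half-width of up to about 11 points.
3. Label the 90% as a patient-level assumption that is not estimated from the pilot, whose 89% is per sector in men with cancer.
4. Replace the 1% for the location-level specificity with an interval that allows for clustering within patients, and state the correlation assumed or a range for it. Use patient-clustered intervals for this endpoint in the analysis.

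The pilot 89% should not serve as a benchmark for the location-level result: it comes from a different tool, a different partition of the gland and men who all had cancer.

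The cost is a rewording of C.4 and a short recalculation, with no extra patients, readers or biopsies. The downside is that the stated precision becomes less favourable.

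### Section C.4 labels intervals of about one standard error as 95% confidence intervals: true 95% half-widths are 8.9 points for sensitivity (5 stated) and 6.5 for specificity (4 stated)

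*Combined protocol and SAP*

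**What the plan says.** Section C.4 (Statistical power consideration) expects "AUC 0.90±0.03, sensitivity 90±5%, specificity 90±4" (the last figure in per cent). On the source of the error terms it says "Variances are estimated based on the expectation of PCa diagnosis in 35% of 125 patients", with binomial probability for sensitivity and specificity. For AUC the variance is "based on an empirical rule-of-thumb formula", which is not identified.

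C.4 then states: "The estimated 95% confidence intervals (CIs) are: for AUC [0.87, 0.93], for sensitivity [0.85, 0.95], and for specificity [0.86, 0.94"]. It adds that these figures leave out the analysis by sextant and zone, and that "estimates of 12 by-location-analyses per patient reduce all uncertainties to about 1" per cent. It concludes: "These estimates suggest that this protocol will produce meaningful performance estimates".

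Section C.3 says of the endpoints: "We will evaluate these performance endpoints on clinically significant PCa (but we will have data for all tumors").

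**The concern.** The half-widths of the stated 95% intervals (0.03, 0.05, 0.04) are the same numbers as the error terms attached to the expected values. With about 44 positive and 81 negative patients, error terms of that size look like standard errors. A 95% interval needs about twice that width.

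C.4 holds the only precision figures given for 125 patients, and its closing judgement rests on them. A reader would expect sensitivity to be known to within 5 points when about 9 is realistic. AUC, the primary endpoint, is affected in the same direction.

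**Working it through.** **Inputs (all from C.4).** N = 125; share positive 0.35; expected sensitivity, specificity and AUC all 0.90; binomial variance for sensitivity and specificity. Hence n+ = 0.35 × 125 = 43.75 and n− = 125 − 43.75 = 81.25.

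**The plan's own intervals.** 0.90 ± 0.03 = [0.87, 0.93]; 0.90 ± 0.05 = [0.85, 0.95]; 0.90 ± 0.04 = [0.86, 0.94]. All three are reproduced by using the error terms directly, with no multiplier.

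**Sensitivity and specificity.** SE = √(p(1−p)/n), with p(1−p) = 0.90 × 0.10 = 0.09. Half-width = 1.96 × SE. Nominal coverage of a stated half-width h is 2Φ(h/SE) − 1 (normal approximation).

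| | Sensitivity | Specificity |
|---|---|---|
| SE | √(0.09/43.75) = 0.0454 | √(0.09/81.25) = 0.0333 |
| 95% half-width | 0.0889 | 0.0652 |
| Stated half-width | 0.05 = 1.10 SE | 0.04 = 1.20 SE |
| Correct / stated | 1.78 | 1.63 |
| Coverage of stated interval | 73% | 77% |
| Wald 95% | [0.81, 0.99] | [0.83, 0.97] |
| Wilson 95% | [0.78, 0.96] | [0.82, 0.95] |

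**Other readings.**
- 80% intervals are already wider than stated: 5.8 and 4.3 points.
- Using all 125 patients as the denominator for each measure, which is not legitimate, gives 1.96 × √(0.09/125) = 5.3 points.
- A 95% half-width of 5 points needs 1.96² × 0.09/0.05² = 138.3, so 139 positives. A half-width of 4 points needs 1.96² × 0.09/0.04² = 216.1, so 217 negatives. Each exceeds the 125 patients to be enrolled.

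**AUC (formula assumed, because C.4 names none).** With A = 0.90:
- Binomial on all patients: √(0.09/125) = 0.0268; half-width 0.053.
- Hanley-McNeil: Q₁ = A/(2−A) = 0.8182 and Q₂ = 2A²/(1+A) = 0.8526. Variance = [0.09 + 42.75 × (0.8182 − 0.81) + 80.25 × (0.8526 − 0.81)]/(43.75 × 81.25) = 0.00109. SE 0.0330; half-width 0.065; interval about [0.84, 0.96].
- Obuchowski (binormal): SE 0.0366; half-width 0.072.
- Upper bound, binomial on the 43.75 positives: SE 0.0454; half-width 0.089.

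A 95% half-width of 0.03 requires SE = 0.03/1.96 = 0.0153, well below all of these.

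**By-location claim.** Twelve locations in each of 125 patients make 1500. Positive locations can lie only in positive patients, so there are at most 43.75 × 12 = 525.
- Sensitivity, with every location in a positive patient positive and all independent: SE = √(0.09/525) = 0.0131; half-width 2.6 points. Fewer positive locations make it wider.
- Specificity, all independent: between 1500 − 525 = 975 negatives (half-width 1.9 points) and 1500 − 43.75 ≈ 1456 negatives, that is, one positive location per positive patient (half-width 1.5 points).
- Positive within-patient correlation widens all of these.

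**If the 35% means all prostate cancer.** C.3 evaluates endpoints on clinically significant cancer, and the documents give no rate for it. Assume 50% to 80% of the positive patients qualify. Positives fall to between 21.9 and 35. The sensitivity half-width becomes 12.6 to 9.9 points (Wilson [0.71, 0.97] to [0.76, 0.96]) and the specificity half-width 5.8 to 6.2 points.

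**The case against.** The best defence concerns importance. No hypothesis test, power figure or acceptance limit depends on these intervals. The final intervals will come from observed data, and C.4 sets no level of precision that 9 points would fail. That is correct, and it limits the harm to overstated precision. It does not make the label right, and C.4 offers no other precision figure for the chosen sample size.

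Four narrower objections carry some weight:
- How the authors obtained the error terms is inferred. Sensitivity and specificity fit one SE rounded up, whereas 0.03 for AUC is one Hanley-McNeil SE rounded down. Being about one SE describes their size and does not establish their origin.
- The AUC shortfall cannot be fixed exactly without the formula. Only the direction is claimed, and 0.089 is an upper bound rather than a usual choice.
- The 50% to 80% share is an assumption from outside the documents. C.4 speaks of a cancer diagnosis, so all cancer is the natural reading of the 35%. The main result uses the 35% as written.
- The 1% by-location figure might be meant as an SE, since the limiting value of 1.3 points could be rounded to it. That reading is possible, but it relies on the most favourable count of positive locations and on independence, and C.4 states neither.

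**Conclusion.** The concern holds. On C.4's own inputs the 95% half-widths are 8.9 points for sensitivity and 6.5 for specificity, and no interval method or denominator considered recovers 5 and 4. This part needs no outside assumption. The AUC interval is too narrow under every formula tried; its size remains conditional on the formula. The by-location figure is undefined and, for sensitivity, cannot be a 95% half-width. This should be fixed because the sample-size justification rests on it, but it does not invalidate the design or the planned analysis.

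**What to change.** Change C.4 only, keeping 125 patients:

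1. Replace the error terms with standard errors labelled as such: 4.5 points for sensitivity, 3.3 for specificity, and an AUC value with its formula named. Merely relabelling 5 and 4 as standard errors would leave them 10% and 20% too large.
2. Restate the 95% intervals and name the method: about [0.78, 0.96] for sensitivity and [0.82, 0.95] for specificity (Wilson), or [0.81, 0.99] and [0.83, 0.97] (Wald). Recompute AUC with the named formula, for example about [0.84, 0.96] with Hanley-McNeil.
3. Say whether the 35% is all prostate cancer or clinically significant cancer. If it is all cancer, add that sensitivity for significant cancer will be less precise than shown.
4. Say whether the by-location 1% is a standard error or a 95% half-width. Recompute it separately for sensitivity and specificity from stated numbers of positive and negative locations per patient, allowing for within-patient correlation.
5. Rest the closing judgement on the corrected widths.

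The cost is wording and a less favourable precision statement, plus stated assumptions on positive locations per patient and within-patient correlation. Sample size, conduct, endpoints and final analysis stay as they are.

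### C.4's claim that by-location analysis brings all uncertainties to about 1% is unsupported: it clearly fails for sensitivity and, as a 95% half-width, holds for no measure

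*Combined protocol and SAP*

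**What the plan says.** Section C.4 expects "AUC 0.90±0.03, sensitivity 90±5%, specificity 90±4" per cent. It takes the variances from cancer in 35% of 125 patients, binomial for sensitivity and specificity and, for AUC, "based on an empirical rule-of-thumb formula" that it does not name. It then labels the ranges: "The estimated 95% confidence intervals (CIs) are: for AUC [0.87, 0.93], for sensitivity [0.85, 0.95], and for specificity [0.86, 0.94"]. For analysis by sextant and zone it adds that "estimates of 12 by-location-analyses per patient reduce all uncertainties to about 1" per cent, and concludes that the estimates will be meaningful. It gives no expected number of positive locations and no within-patient correlation, and does not say whether 1% is an SE or a 95% half-width.

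Section C.3 sets the by-location reference standard: "biopsy sites that do not yield PCa diagnosis will be considered as negative for PCa". It does not say how intervals will allow for several sites from one patient.

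The only by-location counts are in A.3.2: "A sector-based analysis (18 sectors per prostate) on the 17 test patients" gave "sensitivity 75% (105/140), specificity 89% (147/166").

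**The concern.** Twelve locations per patient give 1,500 locations, but sensitivity is estimated only from the positive ones. Under C.3 a cancer patient contributes as many positives as there are sites with cancer, not 12. A precision figure that multiplies both groups by 12 therefore overstates the information on sensitivity. It also treats locations from one prostate as independent.

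The 1% sentence comes directly before C.4's conclusion that the estimates will be meaningful, and AUC is the primary endpoint. A reader would take 1% as the precision to expect from the by-location results and, because the preceding ranges are labelled 95% intervals, would probably read it on that scale. If the final analysis used the same independence assumption, the reported intervals would be too narrow.

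**Working it through.** **Inputs.** From C.4: 125 patients, 35% with cancer (0.35 × 125 = 43.75 with, 81.25 without), 0.90 for each measure, and 12 locations per patient (1,500 in all). From C.3: benign sites are negative. From A.3.2: 140 positive and 166 negative sectors, 306 in all (17 × 18).

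**Formulas.** Sensitivity and specificity: SE = √(0.9 × 0.1 / n). For AUC (A = 0.90), with n₁ positives and n₀ negatives: SE² = [A(1−A) + (n₁−1)(Q₁−A²) + (n₀−1)(Q₂−A²)] / (n₁n₀). C.4 does not name its AUC formula, so I used two:
- Hanley-McNeil: Q₁ = A/(2−A) = 0.818 and Q₂ = 2A²/(1+A) = 0.853.
- Equal-variance binormal: Q₁ = Q₂ = 0.832, the probability that two standard normals with correlation 0.5 both fall below the 0.90 quantile.

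The 95% half-width is 1.96 × SE.

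**Step 1: the per-patient ranges.**
- Sensitivity: √(0.09/43.75) = 4.5%, half-width ±8.9.
- Specificity: √(0.09/81.25) = 3.3%, half-width ±6.5.
- AUC: 3.3% (Hanley-McNeil) or 2.8% (binormal), half-width about ±6.5 or ±5.5.

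C.4's ±5, ±4 and ±3 are therefore about one SE, not 95% half-widths.

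**Step 2: reproducing about 1%.** Multiply both groups by 12: 525 positive and 975 negative locations, treated as independent. One SE is 1.31% for sensitivity, 0.96% for specificity, and 0.95% or 0.81% for AUC. So the figure reproduces as one SE. As 95% half-widths the same counts give ±2.6, ±1.9, and ±1.9 or ±1.6.

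**Step 3: how many positives this needs.** A sensitivity SE that rounds to 1% (1.5% or less) needs 0.09/0.015² = 400 positives, or 400/43.75 = 9.1 per cancer patient. An SE of 1.0% needs 0.09/0.01² = 900, above the maximum of 525.

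**Step 4: counting positives as C.3 does.** With m positive locations per cancer patient, n₁ = 43.75m and n₀ = 1,500 − n₁. The pilot share gives m = 12 × 140/306 = 5.5, so n₁ = 240 and n₀ = 1,260. The table shows one SE (95% half-width), independent locations:

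| m of 12 | Sensitivity | Specificity | AUC, Hanley-McNeil | AUC, binormal |
|---|---|---|---|---|
| 12 | 1.3% (±2.6) | 0.96% (±1.9) | 0.95% (±1.9) | 0.8% (±1.6) |
| 5.5 (pilot) | 1.9% (±3.8) | 0.85% (±1.7) | 1.4% (±2.7) | 1.05% (±2.1) |
| 3 (assumed) | 2.6% (±5.1) | 0.8% (±1.6) | 1.8% (±3.6) | 1.4% (±2.7) |
| 2 (assumed) | 3.2% (±6.3) | 0.8% (±1.6) | 2.2% (±4.4) | 1.65% (±3.2) |
| 1 (assumed) | 4.5% (±8.9) | 0.8% (±1.5) | 3.1% (±6.1) | 2.3% (±4.5) |

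**Step 5: within-patient correlation.** The protocol gives none; 0.3 is assumed here, at m = 5.5.
- Sensitivity: design effect 1 + 4.49 × 0.3 = 2.35, so SE = 1.94% × √2.35 = 3.0%.
- Specificity: cancer patients contribute 6.5 negatives and the others 12, a size-weighted mean of 10.8. The design effect is 1 + 9.76 × 0.3 = 3.93, so SE = 0.85% × √3.93 = 1.7%.
- AUC: a binormal simulation with a shared patient effect (4,000 replicates) moved the SE from 1.03% to 1.39%.

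**The case against.** C.4 says only about 1%, so rounding is allowed. On that tolerance 12 of 12 positives is not strictly required: sensitivity is 1.43% at 10 of 12 and 1.51% at 9. Specificity stays between 0.8% and 1.0% at any count if locations are independent, and AUC at the pilot share is 1.05% or 1.4%. All of this stands. The one-SE claim therefore fails clearly only for sensitivity, and the documents do not settle whether it fails for AUC, because C.4 names no variance formula.

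The pilot share is also a loose guide. It rescales 18 sectors to 12 locations in a preoperative cohort. A coarser grid would tend to raise the positive share and needle sampling to lower it, so the direction of any bias is unknown.

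A reader might infer more than the documents support:

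- **That by-location sensitivity is 4.5 times, or AUC 3.1 times, less precise than claimed.** Those multiples need one positive location per cancer patient, which no section states. The rows for 1 to 3 positives are scenarios only.
- **That the two-site limit bounds sensitivity.** Section B says that the tool "will identify up to two potential clinically significant tumor sites". No section makes that list the by-location call. The ROC endpoint implies a graded output, the pilot map was scored across sectors against a threshold, and a site may span more than one location.
- **That the sample size is undermined.** No sample-size derivation, hypothesis test or success threshold rests on the 1%, and C.4's conclusion also draws on the per-patient figures.

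**Conclusion.** The sentence is wrong as written, because it says all uncertainties. It holds for the three measures together only as one SE, with independent locations and about 9 to 10 or more of 12 positive in every cancer patient, a premise at odds with C.3's counting rule and the pilot counts. At the pilot share, the sensitivity SE is about twice the stated 1%. About 1% as a 95% half-width is reached for no measure, even with all 12 locations positive.

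The per-patient mislabelling does not depend on the pilot share or on any correlation. From C.4's own inputs, the sensitivity interval should be about ±8.9 points rather than ±5, specificity ±6.5 rather than ±4, and AUC about ±5.5 to ±6.5 rather than ±3 (in hundredths).

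The by-location sizes rest on 5.5 positives of 12 and on independence. Fewer positives, or positive correlation of the assumed size, would widen the sensitivity interval. The fault lies in stated precision and does not bias any estimate.

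**What to change.** In C.4:
- Delete the statement that all uncertainties fall to about 1%.
- Restate by-location precision separately for AUC, sensitivity and specificity, from a stated expected number of positive locations per cancer patient, a named AUC variance formula and a stated within-patient correlation, with a range for the two assumed quantities.
- Put per-patient and by-location figures on one labelled scale and correct the per-patient 95% intervals to the half-widths in Step 1. If ±3, ±5 and ±4 are kept, label them as approximate SEs.

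In C.3, state that per-tumor and per-location intervals will use a patient-clustered variance, such as a bootstrap that resamples patients.

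The cost is wording in two sections, a standard variance method, and a justified choice of positive count and correlation. The stated and reported intervals become wider. Enrolment, procedures and point estimates are unchanged.
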